13. SAFETY MANAGEMENT

13.1 Regulatory and Ethical Considerations

13.1.1 Data and Safety Monitoring Plan

The Inova PI will monitor and review the study progress, participant safety, and the accuracy and security of the data. This will be a minimal risk study. The risks of participation are limited to unexpected loss of confidential PHI.

13.1.1.1 Communication Plan

This is a single center study. There are no collaborating institutions.

13.1.2 Risk Assessment

The research interventions include on-label use of two FDA approved defibrillators for DCCV of AF. These procedures include the risks of asystole, arrhythmia, stroke and skin burn or irritation. These risks are present whether or not these procedures are performed as part of a research study. The only risk associated with participation in the study is accidental loss of PHI. This risk will be minimized by temporarily storing the paper case report forms in secure locations and long-term storage of all data in a REDCAP database with shredding of the paper case report forms.

13.1.3 Potential Benefits of Trial Participation

There is no benefit to individual participants in the research study,

PI: [name]

however, the study results will inform IHVI and all other hospitals if there are clinical differences in efficacy or safety of the two commercially available defibrillators. These findings may improve the likelihood of successful and safe DCCV for our future patients as well as patients cared for in hospitals around the world. The results will be reported on clinicaltrials.gov where they will be available to the device manufacturers and the FDA. The results will also be published in a peer reviewed manuscript and presented at a major society meeting.

13.1.4 Risk-Benefit Assessment

Overall risks to research participants are minimal and limited to potential loss of PHI. The benefit of participation is improvement in our knowledge of the mechanism of cardioversion and improvement in the safety and efficacy of this commonly performed procedure. Because the benefits of the study far outweigh the minimal risks, we are justified in pursuing the study.

13.2 Clinical Adverse Events

Clinical adverse events (AEs) will be monitored throughout the study.

13.2.1 Adverse Events Reporting

Since the study procedures are not greater than minimal risk, significant adverse events (SAEs) are not expected. If any unanticipated problems related to the research involving risks to participants or others happen during this study (including SAEs), they will be reported to the IRB in accordance with [Policy – Reporting of Adverse Events, Unanticipated Problems and Protocol Violations, ORI 11.16.](#) AEs that do not meet prompt reporting requirements will be summarized in the narrative or other format and will be tracked and documented internally by the study team but not submitted to the IRB.

The investigator will comply with the requirements of ORI policy and of the reviewing IRB of record for the reporting of protocol deviations, adverse events, and unanticipated problems presenting risk to participants or others (UPIRSOs) to the IRB. If the Inova IRB is not the IRB of record, the Investigator must still submit prompt reports of any potential serious or continuing non-compliance or UPIRSOs to the Inova IRB via the electronic submission system consistent with ORI policy.

13.2.2 Follow-Up Report to and from IRB

The investigator is responsible for ensuring that all SAEs are followed until either resolved or stable

14. PARTICIPANT COMPENSATION AND REPORTS

14.1 Participant Compensation: Not Applicable

14.2 Reporting Events to Participants

14.2.1 Adverse Events Not Applicable

14.3 Study Results and Incidental Findings

14.3.1 Study Results- Study results will be published in peer reviewed manuscripts, society meetings, and on clinicaltrials.gov where they can be seen by study participants.

14.3.2 Incidental Findings Not applicable

15. ECONOMIC BURDENS AND COMPENSATION / INCENTIVE

15.1 Foreseeable Costs

15.1.1 Economic Burden to Participants

We expect no financial or economic burden for the participants

15.2 Payments / Reimbursements

Not applicable

15.2.1 Reimbursement for Travel, Parking and Meals Not applicable

15.2.2 Payments to Parent/LAR for the Time and Inconvenience (i.e. compensation) Not applicable

15.2.3 Payments to Participants for Time, Effort and Inconvenience (i.e. compensation Not applicable

15.2.4 Gifts Not applicable

16. CONSENT PROCESS

16.1 Informed Consent- We have applied for a waiver of documentation of informed consent and alteration of HIPPA

16.1.1 Waiver of documentation of Informed Consent- Please see the completed request within the electronic submission system. Patients will be provided an opt-out information sheet about the study but will not be asked to sign an informed consent form.

16.2 HIPAA Research Authorization(s)

The Inova Health System uses a stand-alone HIPAA Research Authorization that is compliant with federal, state and institutional Privacy rules and regulations.

16.2.1 Alteration of HIPAA Authorization- We have submitted an alteration of

PI: [name]

HIPPA authorization. Please see the request for alteration of HIPPA authorization within the electronic submission system. Patients will be given an information sheet discussing this alteration of HIPPA authorization with the ability to opt-out of participation if desired.

16.3 Safeguards for Vulnerable Populations

- 16.3.1 Cognitively Impaired Individuals- Will not be enrolled in the study.
- 16.3.2 Pediatric Participants- Children will not participate in the study
- 16.3.3 Individuals with Limited English Proficiency- Will be enrolled in the study using a translated information sheet. This will be submitted as an amendment and patients with limited English proficiency will not be enrolled until this is approved.
- 16.3.4 Adults Unable to Consent- Since consent will not be required, adults unable to consent will be enrolled.

16.4 Documentation of Consent: A waiver of documentation of consent has been submitted.

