Atrial fibrillation (AF) is a major cause of cardiovascular morbidity and mortality, affecting more than 46 million people worldwide.¹ Direct current cardioversion (DCCV) is used to terminate an episode of symptomatic or hemodynamically unstable AF. The success rate for DCCV is 90-95% and is dependent on patient and procedural characteristics including obesity, use of antiarrhythmic drugs, pad placement, type of shock waveform and shock energy. Biphasic defibrillation waveform shocks improve DCCV success rates for AF to normal sinus rhythm (NSR) compared to monophasic shocks. Various biphasic shock waveforms are available: The Rectilinear Biphasic Waveform (RBW) is used by the Zoll series R defibrillator while the Biphasic Truncated Waveform (BTW) is used in the FDA approved Lifepak model 15 and 20 defibrillators. Despite their routine use in clinical practice, no adequately powered prospective head-to-head randomized controlled trials (RCT) have compared the safety or efficacy of the two biphasic waveforms for DCCV of AF to NSR.

The primary objectives for this pragmatic prospective randomized controlled trial are to 1) compare the efficacy of first shock DCCV from AF to NSR using anterolateral pad placement and a full-output 200J RBW synchronized shock from a Zoll series R defibrillator or a full output 360J BTW synchronized shock from a Lifepak 15 or 20 defibrillator; 2) compare the DCCV efficacy of first or second full output shock 3) compare the DCCV efficacy of third or fourth full output shock after treatment group cross over after first failing 2 consecutive full output shocks from the originally assigned treatment group. The secondary objective is to compare the frequency of skin irritation or damage after first or second shock cardioversion from either defibrillator.

Data will be derived from approximately 560 patients arriving to Inova sites of care in AF scheduled to undergo either AF ablation with expected DCCV or elective stand-alone AF DCCV. Patients will be included if they are in AF prior to their procedure and are willing to sign the consent form and comply with the research procedures. Participants will be excluded if they are in a rhythm other than AF on arrival to IHVI, have not been appropriately anticoagulated with warfarin or direct oral anticoagulant, or have known left atrial appendage thrombus prior to their procedure.

ABBREVIATIONS AND DEFINITIONS

Abbreviation	Definition of Terms
DCCV	Direct Current Cardioversion

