7.4 Vulnerable Populations

Vulnerable populations will not be enrolled in this study. Both men and women of all races and ethnic groups are eligible for this trial.

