8. RECRUITMENT METHODS

8.1 Methods

8.1.1 Recruitment

Patients in AF presenting to the pre-procedure holding areas prior to DCCV or catheter ablation of AF at Inova care sites will be screened for possible enrollment. Patients will be provided an opt-out information sheet before being enrolled in the study.

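### Section 16.3.4 enrols adults unable to consent, whom Sections 7.4 and 16.3 together exclude and who cannot use the opt-out that replaces signed consent

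*Combined protocol and SAP*

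**What the plan says.** Section 16.3 (Safeguards for Vulnerable Populations) has four items. Two matter most here:

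- 16.3.1: "Cognitively Impaired Individuals- Will not be enrolled in the study".
- 16.3.4: "Since consent will not be required, adults unable to consent will be enrolled".

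Section 7.4, within Participant Selection, says: "Vulnerable populations will not be enrolled in this study". It does not define the term.

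On consent, Section 9.1.1 seeks an alteration of consent, a waiver of its documentation and an alteration of HIPAA authorization. Section 16.1.1 describes what patients receive: "Patients will be provided an opt-out information sheet about the study but will not be asked to sign an informed consent form". Section 8.1.1 fixes the timing: "Patients will be provided an opt-out information sheet before being enrolled in the study". Section 16.2.1 says that the sheet comes "with the ability to opt-out of participation if desired".

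The abstract still describes eligible patients as those who "are willing to sign the consent form and comply with the research procedures".

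**The concern.** Sections 7.4 and 16.3.4 give opposite answers on whether an adult who lacks capacity can be enrolled. This is a stated enrolment rule in conflict with another stated rule, not a missing detail.

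Two things are at stake. The first is the definition of the study population, which depends on which section the enrolling physician follows. The second is participant protection. Without a signed form, the information sheet and opt-out are the safeguard that the protocol describes, and 16.3.4 admits the people who cannot use it.

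**Working it through.** No arithmetic applies. The check is to set the current statements side by side and see whether one reading satisfies them all.

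| Place | Group addressed | Outcome |
|---|---|---|
| 7.4 | Vulnerable populations (undefined) | Not enrolled |
| 16.3.1 | Cognitively impaired individuals | Not enrolled |
| 16.3.3 | Limited English proficiency | Enrolled only after a translated sheet is approved |
| 16.3.4 | Adults unable to consent | Enrolled |
| 7.1, 7.2 | No mention of capacity or cognitive impairment | Silent |

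**Step 1: does 7.4 cover the group in 16.3.4?** Section 7.4 gives no definition, but the heading of 16.3 places adults unable to consent among vulnerable populations. On the protocol's own classification, 7.4 excludes them and 16.3.4 includes them.

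**Step 2: does 16.3.1 conflict as well?** For an adult with dementia who cannot consent, yes: 16.3.1 bars the patient and 16.3.4 enrols the patient. For an adult who lacks capacity for some other reason, 16.3.1 is silent and the conflict is with 7.4 alone.

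**Step 3: does the opt-out work for this group?** Under 8.1.1, 16.1.1 and 16.2.1 the patient receives the sheet before enrolment and may decline. Someone who cannot understand the sheet cannot act on it. None of these sections names a representative to receive it or to opt out. Section 16.3.3 shows that the protocol itself treats understanding the sheet as a precondition: patients with limited English wait for a translation. The next item drops that precondition for people whom no translation would help.

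**Step 4: would another part of the plan catch the conflict?** Not reliably.

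- The criteria in 7.1 and 7.2 contain no capacity test. Section 7.2.1.2 lets the investigator exclude people thought likely to be non-compliant, which is a different matter.
- Section 8.1.2 says eligibility is the same as for clinical cardioversion, so no extra chart review is needed, and leaves screening to the physician performing the procedure.
- Section 11.1 says study staff need not be present at enrolment.

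The decision therefore rests with one physician, working from text that answers both yes and no.

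**Step 5: the abstract.** Its phrase "willing to sign the consent form and comply with the research procedures" conflicts with 16.1.1 for every participant, because nobody is asked to sign. It is a separate inconsistency and is not used here as evidence about incapacity.

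**The case against.** The strongest defence reads the sections together. Inability to consent and cognitive impairment are not the same thing, so 16.3.4 might cover only adults who lack capacity for other reasons, with 16.3.1 still barring the cognitively impaired. Section 7.4 sits in the same section as the eligibility criteria and could itself be taken as the controlling exclusion. The protocol also seeks an alteration of consent, not only a waiver of its documentation, and the request is held in an electronic submission system that is not part of these documents. It may cover this group.

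Part of this stands. The narrow reading softens the clash with 16.3.1, and since the scope of the alteration is unknown, the reason given in 16.3.4 cannot be called plainly wrong. The clash with 7.4 remains, because 16.3 itself puts these adults among the vulnerable. The unusable opt-out remains on any reading. If 7.4 is meant to control, 16.3.4 has no function.

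A reader might infer more than the documents support:

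- *That patients already sedated would be enrolled.* The planned order does not produce them. Screening takes place in the pre-procedure holding area with a face-to-face discussion, the sheet comes before enrolment (8.1.1, 8.1.2), and sedation follows connection to the allocated defibrillator (9.2.1).
- *That these patients' data would later be removed, costing evaluable patients or power.* The documents give no count of adults unable to consent and no rule for removing their data, so no such loss can be estimated.
- *That the abstract's signing requirement is a further rule excluding this group.* It conflicts with the no-signature process for everyone.

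**Conclusion.** The contradiction is real and stands in current text. There are two opposed outcomes: Section 7.4, read with the heading of 16.3, excludes adults unable to consent, and 16.3.4 enrols them. Section 16.3.1 adds a direct conflict for those who are also cognitively impaired. Followed as written, 16.3.4 would randomise people who cannot use the opt-out and for whom nobody is named to use it.

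The number of patients is unknown, and no consequence for the sample size or the primary comparison can be shown. The point should be corrected because it decides who may be enrolled and how they are protected, and because the correction is cheap. It rests on two assumptions: that the heading of 16.3 shows what the protocol means by vulnerable, and that staff would act on 16.3.4 as worded. Confidence is high for the textual conflict and the missing opt-out route. It does not extend to how often such patients would present.

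**What to change.** - **Section 16.3.4:** change it to *Adults unable to consent will not be enrolled*, consistent with 7.4 and 16.3.1.
- **Section 7.2:** add the exclusion *lacks capacity to understand the information (given in writing or explained) and to opt out before randomisation*. The test should be capacity, not reading ability, because no section bars adults with capacity who cannot read.
- **If the sponsor does intend to enrol these adults:** reconcile 7.4 and 16.3.1 with 16.3.4 instead, and name a representative who receives the sheet and can opt out before randomisation.
- **Separately:** replace the abstract's wording on signing a consent form so that it matches 16.1.1, for example *given the information sheet and did not opt out*.

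The cost is wording in one amendment. Under the first option the trial loses a group of unknown but probably small size that 7.4 already excludes.

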16.5 STUDY INTERVENTION DISCONTINUATION AND PARTICIPANT DISCONTINUATION / WITHDRAWAL

Participants may withdraw from the study at any time without prejudice to their care. They may also be discontinued from the study at the discretion of the Investigator for lack of adherence to study treatment or visit schedules, AEs, or due to reasons listed below. The Investigator or Sponsor may also withdraw participants who violate the study plan, or to protect the participant for reasons of safety or for administrative reasons. It will be documented whether each participant completes the study. If the Investigator becomes aware of any serious, related adverse events after the participant completes or withdraws from the study, the participants will be communicated based on the IRB's directions.

16.6 Discontinuation of Study Intervention

Discontinuation from study intervention does not mean discontinuation from the study, and remaining study procedures should be completed as indicated by the study protocol. If a clinically significant finding is identified (including, but not limited to changes from baseline) after enrollment, the investigator or qualified designee will determine if any change in participant management is needed. Any new clinically relevant finding will be reported as an adverse event (AE).

16.7 Participant Discontinuation/Withdrawal from the Study

Participant may voluntarily withdraw from the study or discontinue the study intervention at any time.

Participants may discontinue the study intervention, but remain in the study for follow-up, especially for safety and efficacy of study endpoints

A Pragmatic Randomized Clinical Trial Comparing Rectilinear Biphasic Waveform and Biphasic Truncated Exponential Waveform Shocks for Cardioversion of Atrial Fibrillation (Zoll vs Lifepak-RCT) |

PI: [name]

An Investigator may discontinue or withdraw a participant from the study for the following reasons:

- 16.7.1 Significant study intervention non-compliance.
- 16.7.2 Any Clinical Adverse Event (AE), laboratory abnormality, or other medical condition or situation occurs such that continued participation in the study would not be in the best interest of the participant.
- 16.7.3 Disease progression which requires discontinuation of the study intervention.
- 16.7.4 If the participation meets an exclusion criterion (either newly developed or not previously recognized) that precludes further study participation.
- 16.7.5 Participant unable to receive DCCV on the scheduled date/time.

The reason for participant discontinuation or withdrawal from the study will be recorded on the paper Case Report Form (CRF).

17. RECORDINGS

NA

18. IRB REVIEW HISTORY

NA

19. COORDINATING CENTER FOR MULTI-SITE STUDIES

19.1 Participating Sites

NA

19.2 Description of Collecting Sites

NA

19.3 Study-Wide Number of Participants

560

